### **8.3.7. Clinical Global Impression-Improvement (CGI-I)**

The Clinical Global Impression-Improvement (CGI-I) score will be collected on Day 8, Day 15, Day 29, Day 43, Day 56, and Day 70. CGI-I consists of one question, where the clinician is asked, “Compared to his condition at admission to the project, how much has he changed?” This question is rated on a scale from 0 to 7, where a higher score indicates greater lack of improvement, as follows:

- 0 = Not assessed
- 1 = Very much improved
- 2 = Much improved
- 3 = Minimally improved
- 4 = No change
- 5 = Minimally worse
- 6 = Much worse
- 7 = Very much worse

A CGI-I improver is defined as a subject with a CGI-I score of “Very much improved” or “Much improved”.

A categorical summary of CGI-I improvers (Yes, No) will be displayed at all scheduled post-baseline visits. A value of “Not assessed” will be treated as missing and not included in the categorical summary.

A listing of the CGI-S and CGI-I scores will also be provided.

### **8.3.8. Patient Global Impression-Improvement (PGI-I)**

The Patient Global Impression of Improvement (PGI-I) score will be collected on Day 8, Day 15, Day 29, Day 43, Day 56, and Day 70. PCGI-I consists of one question where the subject is asked to describe his or her current condition with how it was before treatment. This question is rated on a scale from 0 to 7, where a higher score indicates greater dissatisfaction with treatment, as follows:

- 0 = Not assessed
- 1 = Very much better
- 2 = Much better
- 3 = A little better
- 4 = No change
- 5 = A little worse
- 6 = Much worse
- 7 = Very much worse

Summary statistics on the observed and change from baseline in the PGI-I score will be displayed at baseline and Day 56. A value of zero will be treated as missing and not included in the summary statistics.

A listing of the PGI-I score will also be provided.

#### **8.4. Exploratory Efficacy Analysis**

The exploratory efficacy objective of this study is to evaluate subject-reported changes in depression and anxiety symptoms.

##### **8.4.1. Hamilton Depression Rating Scale (6-item) (HAMD-6)**

The Hamilton Depression Rating Scale (6-item) (HAMD-6) measures six core symptoms of depression on a 0-4-point scale for items 1 to 5 and 0-2 points for item 6. The total score is calculated by summing the 6 item scores and will range from 0 to 22. A higher score indicates more severe depression.

All HAMD-6 summaries, listings, figures, and analyses will be described in a separate analysis plan and performed separately by an external vendor.

##### **8.4.2. General Anxiety Disorder (7-item) (GAD-7)**

The General Anxiety Disorder (7-item) (GAD-7) Scale consists of 7 items scored on a 4-point scale. The total score is calculated as the sum of all item scores and ranges from 0 to 21. A higher score indicates more severe anxiety.

All GAD-7 summaries, listings, figures, and analyses will be described in a separate analysis plan and performed separately by an external vendor.

### **9. Safety Analysis**

The primary safety objectives of this study are to evaluate the overall safety of ANC-501 capsules in subjects with MDD. There will be no imputations for missing data except as outlined in Section 5.1 of this SAP.

The safety endpoints will be summarized using descriptive statistics. All safety analyses will be based on the safety population.

Results for safety parameters will also be listed by subject according to the relevant section in this SAP.

## 9.1. Safety Parameters

Primary parameters for safety to be considered include:

- Frequency and severity of adverse events (AEs)
- Vital signs
- Body weight
- Electrocardiograms (ECGs)
- Clinical laboratory tests
- Physical examination
- Lens Opacities Classification System III (LOCS III)
- Emergent behavior using Columbia-Suicide Severity Rating Scale (C-SSRS)

The secondary safety parameter is the plasma concentrations of ANC-501.

Exploratory parameters for safety to be considered include:

- Changes in 12-hour urine, plasma, and saliva cortisol from baseline to Day 56
- Changes in biometrics using the wearable watch-like device
- Baseline levels and/or changes in exploratory biomarkers through Day 56

## 9.2. Primary Safety Analysis

The primary safety objective of this study is to evaluate the safety and tolerability of ANC-501 capsules in subjects with MDD.

### 9.2.1. Adverse Events

Adverse events (AEs) summaries will only consider treatment-emergent adverse events (TEAEs), using the safety population. TEAEs are defined as those AEs that occurred after dosing and those existing AEs that worsened during the study. If it cannot be determined whether the AE is treatment-emergent due to an incomplete or missing onset date or time, the AE will be considered a treatment-emergent AE. AEs with an onset day after the last day study medication was applied will not be considered TEAEs.

An overall categorical summary of TEAEs will be provided where the total number of TEAEs, the number and percent of subjects with at least one mild, moderate, or severe TEAE, and the number and percent of each of the following items will be displayed:

- Subjects with at Least One TEAE
- Subjects with at Least One TEAE Related to Study Treatment
- Subjects with at Least One TEAE Leading to Discontinuation of Study Treatment

- Subjects with at Least One TEAE of Special Interest
- Subjects with at Least One Serious TEAE
- Subjects with at Least One TEAE Leading to Death

AEs of Special Interest and Related AEs are defined as stated in Section 5.2 of this SAP. If a subject reports one or more events within the same SOC and PT, the subject is classified (Related/Not Related) according to the most related relationship within the same SOC and PT.

In addition, for each bulleted item in the above list, categorical summaries for TEAEs by system organ class (SOC) and preferred term (PT) via MedDRA version 25.0 will be provided, and subjects having more than one TEAE may appear in more than one SOC or PT but will be counted at most once per each SOC and PT. Furthermore, a summary of TEAEs by SOC, PT, and maximum relatedness (Related, Not Related) will be provided where the maximum relatedness will be used for subjects with multiple TEAEs within the same SOC and PT, and a summary of TEAEs by SOC, PT, and maximum severity (Mild, Moderate, Severe) will be provided where the maximum severity will be used for subjects with multiple TEAEs within the same SOC and PT. Summaries that are displayed by SOC and PT will be ordered by descending incidence of SOC and then PT within each SOC, and if applicable ascending severity within SOC and PT.

A listing of adverse events and a listing of serious adverse events will also be provided.

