## **5.1. Handling Missing Data**

For incomplete dates related to adverse events and concomitant medications, the dates will be imputed as follows:

- Incomplete start dates missing day with known month will be imputed as the later of (a) day of first dose started in that month or (b) first of the month.
- Incomplete start dates missing month and day will be imputed as the later of (a) month and day of first dose started in that year or (b) January 1.
- Dates missing year regardless of month or day will be considered as missing.
- An unknown start time with known or imputed date will be imputed with a time of 23:59 for events or medications on Day 1 or as 00:00 on other days.
- An unknown end time with known or imputed date will be imputed the same as a missing start time unless the event or medication is ongoing.
- Events with completely unknown start dates will be considered as treatment-emergent adverse events unless otherwise indicated by a known end date.
- Medications with completely unknown start dates will be considered as concomitant medications unless otherwise indicated by a known end date.
- Any imputed start date or time must come before any known end date or time.
- Missing dates, date parts, and time will be shown as missing in the listings.

For missing values not described in this section of the SAP, imputation will not be performed.

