## **5.2. Definitions**

- The baseline measurement for a variable is defined as the most recent non-missing value prior to study treatment.
- The change from baseline measurement for a variable at a post-baseline visit will be derived as the measurement taken at the specified visit minus the baseline measurement.
- Treatment Duration will be derived as the total number of days on treatment as follows: Date of Last Dose – Date of First Dose + 1.

- Study Duration will be defined as the total number of days in the study as follows: Date of Last Visit – Date of Informed Consent + 1.
- Treatment Period is defined to be the period that the subject is active on treatment: Date of First Dose through Date of Last Dose.
- Treatment Compliance over the Treatment Period will be calculated as follows based on drug accountability: Treatment Compliance (%) = Number of capsules taken / Number of capsules expected to be taken  $\times$  100.
- Morning Meal Compliance over the Treatment Period will be calculated as follows based on Day 1 administration and the dosing diary: Morning Meal Compliance is Yes if all responses to the following questions are yes; otherwise, Morning Meal Compliance is No:
  - Was subject dosed at least 1 hour prior to morning meal?
  - Since last visit, has subject been compliant with dosing at least 1 hour prior to the morning meal?
- MADRS responders are defined as subjects who experienced a  $\geq$  50% reduction in MADRS total score compared to baseline.
- MADRS remitters are defined as subjects with a MADRS total score  $\leq$  10.
- CGI-I improvers are defined as subjects who reported “Very much improved” or “Much improved” on the CGI-I scale.
- An adverse event is defined as Related if the event is reported as Definitely Related, Probably Related, or Possibly Related.
- Adverse Events of Special Interest are defined as a change from baseline of  $\geq$  0.5 in Nuclear Opalescence, Cortical Lens Opacity, or Posterior Subcapsular Lens Opacity on the LOCS III scale, or any other ophthalmic results deemed clinically significant by the investigator.
- Age at First MDD Diagnosis will be calculated as follows: Year of the First MDD Diagnosis – Year of Birth, where the Year of the First MDD Diagnosis is defined as the year from the earliest start date of the major depressive episodes determined in Section 7.4 of this SAP.

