### 7.1. Subject Disposition

Information regarding subject disposition will be summarized using all subjects. Summaries will include the number of screen failures, the number of enrolled subjects, the number of subjects in the safety and efficacy populations, number of subjects completing the study treatment, number of subjects who discontinue the study treatment early, number of subjects completing the study, and number of subjects who discontinue the study early. For those who discontinue the study treatment early or discontinue the study early, the primary reason for discontinuation will be summarized.

A listing of subjects showing screen failures, analysis populations, study treatment status, study status, reason for discontinuing study treatment early, if applicable, and reason for discontinuing the study early, if applicable, will also be provided. Additionally, a listing of inclusion/exclusion criteria not met will be provided.

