#### **9.2.4. Clinical Laboratory Tests**

Laboratory evaluations (hematology, serum chemistry, coagulation, urinalysis) will be conducted at Screening, Day 1, Day 8, Day 56, and Day 70. Any clinically significant laboratory result after baseline is to be captured as an adverse event and thus included in the summary of adverse events.

Summary statistics for the observed and change from baseline continuous laboratory results will be displayed at baseline and all scheduled post-baseline visits via the following tables:

- Hematology
- Serum Chemistry
- Coagulation
- Urinalysis

For categorical urinalysis results, frequency counts and percentages will be presented.

For laboratory parameters (hematology, serum chemistry, coagulation) where normal ranges are available, shift tables will be presented for all scheduled post-baseline visits. Categories for the shift tables will be Missing, Low, Normal, High, and Total.

A listing for each category of laboratory results shown in the above bulleted list as well as a listing for serology will also be provided, and values will be flagged as Low, Normal, or High relative to normal ranges, if available, and included in the listings. In addition, a listing will be provided for urine drug screen results and a listing will be provided for alcohol breath test screen results.

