#### **9.2.6. Lens Opacities Classification System III (LOCS III)**

An ophthalmic exam including slit-lamp imaging may be performed and would be assessed using LOCS III. Any result that is an AE of Special Interest as defined in Section 5.2 of this SAP is to be recorded.

LOCS III data are collected at Screening, Day 56, Day 70, and Day 112. A summary for change from baseline in four LOCS III parameters (Cortical Lens Opacity, Nuclear Color, Nuclear Opalescence, Posterior Subcapsular Lens Opacity) by eye (OD, OS) at all scheduled post-baseline visits will be provided.

In addition, a shift table for each of the LOCS III parameters by eye will be provided. The possible values for Cortical Lens Opacity (C) range from 0.1 to 5.9, for Nuclear Color (NC) range from 0.1 to 6.9, for Nuclear Opalescence (NO) range from 0.1 to 6.9, and for Posterior Subcapsular Lens Opacity (P) range from 0.1 to 5.9. The exclusion criteria based on LOCS III are as follows:

- C with a LOCS III classification > 2.0 in either eye
- NC with a LOCS III classification > 3.5 in either eye
- NO with a LOCS III classification > 3.0 in either eye
- P with a LOCS III classification > 0.3 in either eye

Given the above exclusion criteria and the definition of AEs of Special Interest as provided in Section 5.2 of this SAP, the categories for the shift tables will be defined as follows, where Nuclear Color will follow the same shift table categorization strategy as Nuclear Opalescence, Cortical Lens Opacity, and Posterior Subcapsular Lens Opacity:

Baseline categorization:

- C: Missing, 0.1 to <= 1.0, > 1.0 to <= 2.0, > 2.0, Total
- NC: Missing, 0.1 to <= 1.5, > 1.5 to <= 2.5, > 2.5 to <= 3.5, > 3.5, Total
- NO: Missing, 0.1 to <= 1.0, > 1.0 to <= 2.0, > 2.0 to <= 3.0, > 3.0, Total
- P: Missing, 0.1 to <= 0.2, > 0.2 to <= 0.3, > 0.3, Total

Post-baseline categorization:

- Change: Missing, <= -0.5, > -0.5 to < 0, No Change, > 0 to < 0.5, >= 0.5, Total

Primary ophthalmic data (assessment of first reading) will be used for summaries, and a listing of primary ophthalmic data will also be provided. Secondary ophthalmic data (secondary readings) will not be summarized or listed.

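### SAP 9.2.1 keeps adverse events that start after the last dose out of every AE table, so follow-up lens events and SAEs are not counted there, and it conflicts with SAP 9.2.4 on Day 70 laboratory AEs

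*SAP*

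**What the plan says.** SAP 9.2.1 states that AE "summaries will only consider treatment-emergent adverse events (TEAEs), using the safety population". It then closes the treatment-emergent period on the final dosing day: "AEs with an onset day after the last day study medication was applied will not be considered TEAEs". The overall table has rows for special-interest, serious and fatal events, each defined as a TEAE, and the SOC/PT tables follow the same rows. Listings of AEs and SAEs are the only outputs in that section that are not limited to TEAEs.

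Other parts of the plan run past that cut-off:

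- **AE collection.** Protocol 8.4.3 collects AEs and SAEs from the first dose to Day 112. Protocol 4.1 places the last dose at the Day 56 visit.
- **Lens exams.** SAP 9.2.6: "LOCS III data are collected at Screening, Day 56, Day 70, and Day 112".
- **Special-interest definition.** SAP 5.2 covers a LOCS III change of at least 0.5 in nuclear opalescence, cortical or posterior subcapsular opacity, "or any other ophthalmic results deemed clinically significant by the investigator". It sets no time limit.
- **Protocol 9.4.2.** LOCS III change is assessed to Days 56, 70 and 112, and qualifying increases are AEs and events of special interest.
- **Laboratory tests.** SAP 9.2.4 says these "will be conducted at Screening, Day 1, Day 8, Day 56, and Day 70", and that a clinically significant result after baseline "is to be captured as an adverse event and thus included in the summary of adverse events".
- **Unknown onset.** SAP 5.1: "Events with completely unknown start dates will be considered as treatment-emergent adverse events unless otherwise indicated by a known end date". SAP 9.2.1 has the same default for onsets too incomplete to classify.

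**The concern.** Frequency and severity of AEs is a primary safety endpoint, and lens opacity is the only designated event of special interest. In the earlier Phase 2 study, two subjects had lens events that met prespecified LOCS III criteria, both at 50 mg, which is the starting dose here (Protocol 2.4). The amendment log attributes both the Day 112 visit for all subjects and the lens-opacity section to FDA comments, and the Day 112 exam is still in the schedule.

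As written, the row counting subjects with a special-interest event omits anything with an onset dated at Day 70 or Day 112. It could show zero subjects while the LOCS III shift tables show increases of 0.5 or more at those visits. The labels differ, so this is not a formal contradiction, but no table would give the number of subjects affected. SAEs and fatal AEs that begin in follow-up are left out in the same way. An event with an unclassifiable onset is counted, while one clearly dated after the last dose is not.

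**Working it through.** The plan gives no figure to reproduce here. The check is a count of days and visits, a comparison of two SAP sections, and two small calculations.

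**1. Days and lens visits outside the window (completers).** Inputs: last dose at the Day 56 visit, window Day 53 to 59; Day 70 exam, window 67 to 73; Day 112 exam, window 109 to 115.

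| Quantity | Nominal | Minimum | Maximum |
|---|---|---|---|
| Last dose to Day 70 exam | 70 − 56 = 14 days | 67 − 59 = 8 | 73 − 53 = 20 |
| Last dose to Day 112 exam | 112 − 56 = 56 days | 109 − 59 = 50 | 115 − 53 = 62 |
| Share of AE collection days after last dose | 56/112 = 50% | 50/109 = 46% | 62/115 = 54% |

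Two of the three scheduled post-baseline lens exams therefore fall after the cut-off. The percentages are calendar time, not a proportion of events.

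**2. Early terminators.** Footnote a of the schedule asks for the Day 56 procedures as soon as possible after stopping, then follow-up at 2 and 8 weeks after the ET visit. If the ET exam is held after the last dosing day, all three lens exams fall outside. SAP 4 reports that two subjects were discontinued near the start.

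**3. SAP 9.2.1 against SAP 9.2.4.** After the first dose, laboratory visits are Days 8, 56 and 70 (Day 1 is pre-dose), so one of three falls after the last dose. A laboratory AE with onset at Day 70 belongs in the AE summary under 9.2.4 and is excluded from it under 9.2.1. SAP 11 ranks the SAP over the protocol; it does not rank one SAP section over another.

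**4. What counts a follow-up event elsewhere.**

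- *LOCS III increase of 0.5 or more:* SAP 9.2.6, by eye and by parameter, not by subject.
- *Other clinically significant ophthalmic finding:* listing only.
- *SAE:* listing only.
- *Death:* listing, and as a disposition reason, since SAP 7.1 states "For those who discontinue the study treatment early or discontinue the study early, the primary reason for discontinuation will be summarized" and Protocol 7.2 includes death among the reasons for withdrawal.

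**5. How tight the cut-off is.** Protocol 2.3.1 gives a half-life of about 20 hours. Assuming log-linear decline, the level 24 hours after the last dose is 0.5^(24/20) = 43.5% of the level 24 hours earlier. Five half-lives take 5 × 20 = 100 hours, or about 4.2 days. An AE starting the day after the last dose is excluded while drug is still present.

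**6. Effect on the reported row.** For illustration, assume 20 subjects (the protocol maximum) and no on-treatment special-interest event. Exact (Clopper-Pearson) 95% intervals:

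| Subjects with an event | Percent | 95% CI |
|---|---|---|
| 0/20, as the row would read | 0% | 0 to 16.8% |
| 1/20, with one follow-up event | 5% | 0.1 to 24.9% |
| 2/20, with two follow-up events | 10% | 1.2 to 31.7% |

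For 0/20 the upper limit is 1 − 0.025^(1/20) = 16.8%.

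**The case against.** The best defence is that an on-treatment TEAE window is a legitimate choice and that no data are lost. All AEs and SAEs are listed, SAP 9.2.6 shows LOCS III change at every scheduled visit with a category for increases of 0.5 or more, and with at most 20 subjects a reader can count from the listings. This stands as a limit on the consequence. It does not supply the missing subject-level count, and it does not cover ophthalmic findings without a qualifying LOCS III change.

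Protocol 9.4.2 can be read as governing how lens changes are classified and reported, without requiring a TEAE row. That is fair: the SAP rule undercuts the protocol's intent more than its letter.

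The laboratory conflict arises only when onset is dated after the last dose; an abnormality present by Day 56 and persisting at Day 70 satisfies both sections. That also stands, but a new Day 70 abnormality remains unresolved.

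The half-life argument supports a margin of a few days, not counting to Day 112. Agreed. The case for Day 112 rests on the scheduled lens exams and the AE collection period. The documents also do not say what the FDA comments asked for in the tables.

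Finally, SAP 9.2.1 counts existing AEs that worsen during the study, which might bring in a lens AE that began on treatment and worsened later. However, Protocol 8.4.4.3 records severity changes over days as separate entries with their own onset dates, so the cut-off could remove them again. This is a further ambiguity, not an answer.

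**Conclusion.** The concern holds. Followed as written, SAP 9.2.1 leaves special-interest events, SAEs and fatal AEs with a recorded onset after the last dose out of every AE table, and it cannot be reconciled with SAP 9.2.4 for a new Day 70 laboratory AE. For completers, two of three post-baseline lens exams, one of three post-dose laboratory visits and about half of the AE collection time are affected. For early terminators it can be all three lens exams.

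The visit counts follow from the schedule. The 0/20 to 2/20 comparison rests on assumed event counts and full enrolment. How many lens events would be lost also depends on how onset is entered, which neither document specifies: a Day 70 or Day 112 finding could be dated to the exam or to an earlier day. The gap is in tabulation, not data capture, so it should be corrected but does not threaten the safety data themselves.

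**What to change.** In SAP 9.2.1:

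1. Keep the planned on-treatment TEAE tables.
2. Summarise special-interest events, SAEs and AEs leading to death from first dose through the Day 112 visit. The special-interest summary should give n (%) of subjects meeting the full SAP 5.2 definition in either eye at any post-baseline exam, including ET and unscheduled exams.
3. Show other AEs with onset after the last dose in a separate follow-up column or table. This gives Day 70 laboratory AEs a place in the summary and reconciles 9.2.1 with 9.2.4; a cross-reference in 9.2.4 should say so.
4. State how the onset date is assigned when a lens event is found at an exam.

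The cost is SAP wording and one or two extra tables. All the data are already collected and the on-treatment tables do not change. Reported incidence over the whole study may be slightly higher. The change is best made before database lock, because SAP 5 labels later additions post hoc.
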